2. To assess dietary patterns, physical activity, and health-related quality of life of participants in the CREDOenAP program at the end of the intervention and one year later.	
Change in dietary patterns at 6 and 18 months, assessed using a validated 24-hour recall questionnaire, to evaluate adherence to the nutritional component of the intervention.
 
Change in physical activity levels at 6 and 18 months, measured using the International Physical Activity Questionnaire (IPAQ).
 
Change in health-related quality of life at 6 and 18 months, assessed using validated instruments such as the SF-36 or EQ-5D questionnaires.
	
Changes in the scores of the aforementioned questionnaires will allow evaluation of changes in dietary patterns, physical activity, and health-related quality of life.

3. To assess anthropometric, metabolic, and imaging markers for cardiovascular risk evaluation in participants of the CREDOenAP	Change in cardiovascular risk factors at 6 and 18 months, including blood pressure, total cholesterol, HDL cholesterol, LDL cholesterol, Apo B100, triglycerides, and the presence and	These measures will allow evaluation of key underlying mechanisms contributing to type 2 diabetes (T2DM) remission.

program at the end of the intervention (6 months) and one year later (18 months).	size of carotid atherosclerotic plaques. Change in metabolic indicators at 6 and 18 months, assessed through weight, body mass index (BMI), waist circumference, insulin resistance (HOMA-IR), pancreatic beta-cell function (HOMA-B), and fasting insulin levels.	
Tertiary/Exploratory		

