To assess secondary metabolic markers for cardiovascular risk evaluation in participants of the CREDOenAP program at the end of the intervention (6 months) and one year later (18 months). To assess healthy lifestyle habits and health-related quality of life patterns in participants of the CREDOenAP program at the end of the intervention and one year later.	Change in metabolic indicators at 6 and 18 months, assessed through the diagnosis of Metabolic Syndrome, NAFLD Fatty Liver Index, and NAFLD Fibrosis Score. Change in healthy lifestyle habits at 6 and 18 months, assessed through smoking habits (custom questionnaire), alcohol consumption (questionnaire and conversion calculator for standard drink units), and circadian habits (custom questionnaire). Change in quality of life at 6 and 18 months, assessed through medication use measured as Defined Daily Dose (DDD) of the active ingredient.	These measures will allow evaluation of secondary underlying mechanisms for T2DM remission. Changes in the scores of the aforementioned questionnaires and indicators will allow evaluation of changes in healthy lifestyle habits and quality of life.

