All secondary outcome variables will be measured, calculated, and recorded at study baseline, at the end of the intervention, and 12 months after the intervention.

a) Cardiovascular Risk Factors

- **Blood pressure:** Blood pressure will be measured three times after the participant has been seated at rest for 10 minutes with uncrossed legs. The mean of the last two measurements will be used for statistical analysis. Systolic and diastolic blood pressure will be reported in mmHg using a brachial cuff sphygmomanometer.
- **Total cholesterol:** Measured in mg/dL via blood analysis.
- **HDL cholesterol:** High-density lipoprotein (HDL) cholesterol measured in mg/dL via blood analysis.
- **LDL cholesterol:** Low-density lipoprotein (LDL) cholesterol measured in mg/dL via blood analysis.
- **Apolipoprotein B100 (ApoB100):** A protein involved in cholesterol transport and relevant for evaluating elevated cholesterol causes, measured in mg/dL via blood analysis.
- **Triglycerides:** Measured in mg/dL via blood analysis.
- **Presence and size of atherosclerotic plaques in carotid arteries:** Assessed via Carotid ultrasonography. If plaques are present, the total plaque area will be measured in cm², and changes in plaque area will be tracked throughout the study.

b) Metabolic Indicators

- **Weight:** Measured in kilograms using a calibrated scale.
- **Body Mass Index (BMI):** Calculated from weight and height using the formula: BMI = weight (kg) / [height (m)]².
- **Abdominal circumference:** Measured at the midpoint between the lowest rib and the iliac crest during maximal inspiration and expiration, in centimeters.
- **Insulin resistance:** Evaluated using the HOMA-IR index (Homeostasis Model Assessment of Insulin Resistance), which estimates insulin resistance and beta-cell function. Determined via blood analysis after a minimum 8-hour fast. Values above 2.5 may indicate T2DM. Calculated as: [fasting insulin (μU/mL) x glucemia basal (mmol/L)] / 22.5 = [fasting insulin (μU/mL) x (Glucemia basal (mg/dL) x 0,0555)] / 22.5 (*HOMA Calculator — Radcliffe Department of Medicine, n.d.*)

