- **Pancreatic activity:** Assessed using the HOMA-B index, which evaluates the function and activity of pancreatic beta cells. HOMA-B, together with HOMA-IR, helps in the diagnosis of T2DM. Values between 167 and 175 are considered normal and not indicative of T2DM. Values below this range suggest impaired beta-cell function, resulting in insufficient insulin production (insulinopenia). (*HOMA Calculator — Radcliffe Department of Medicine, n.d.*)
- **Fasting insulin:** Measures the amount of insulin in a blood sample. Insulin is a hormone produced by the pancreas. Normal values range between 5–25 U/mL. It will be measured via blood analysis after a minimum 8-hour fast.
- **Metabolic Syndrome Diagnosis:** Refers to a cluster of metabolic abnormalities considered a high-risk factor for cardiovascular disease and other health complications. It will be assessed according to the criteria of the International Diabetes Federation (IDF) new classification. (*International Diabetis federation (IDF), 2006*) y National Cholesterol Education Program's Adult Treatment Panel III (NCEP ATP III) (*Alexander et al., 2003*).

Metabolic Syndrome Diagnosis is established if at least three of the following five criteria are present:

- Abdominal circumference: Men of European descent > 94 cm; Women of European descent > 80 cm. For other ethnicities, cut-off points are defined according to the International Diabetes Federation (IDF). (*López De La Torre et al., 2010*)
- Fasting glucose: > 100 mg/dL or receiving pharmacological treatment for hyperglycemia.
- Triglycerides: > 150 mg/dL or receiving lipid-lowering therapy.
- HDL cholesterol: < 40 mg/dL in men; < 50 mg/dL in women, or receiving lipid-lowering therapy.
- Blood pressure: Systolic > 130 mmHg or Diastolic > 85 mmHg, or receiving antihypertensive treatment.

- **NAFLD Liver Fat Score:** Non-alcoholic fatty liver disease (NAFLD) is a condition characterized by excessive fat accumulation in the liver. Its severity can vary according to the score: < -1.455 low risk, -1.455 to 0.675 intermediate risk, > 0.675 high risk (*Angulo et al., 2007; Kotronen et al., 2009*).

The calculation is determined using the following formula:

$$-2.89 + 1.18 \times \text{Metabolic Syndrome (Yes = 1 / No = 0)} + 0.45 \times \text{T2DM (Yes = 2 / No = 0)} + 0.15 \times \text{Fasting Insulin (mU/L)} + 0.04 \times \text{Fasting Serum AST (U/L)} - 0.94 \times \text{AST/ALT ratio}$$

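### Waist circumference is read at two opposite, maximal-effort breathing phases, and the protocol does not say which value is the secondary endpoint or is compared with the metabolic-syndrome cut-offs.

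*Protocol*

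**What the plan says.** In Section 8.1, under metabolic indicators, abdominal circumference is "Measured at the midpoint between the lowest rib and the iliac crest during maximal inspiration and expiration, in centimeters". No other part of the protocol adds to this rule.

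Section 3 makes the variable a secondary endpoint: "Change in metabolic indicators at 6 and 18 months, assessed through weight, body mass index (BMI), waist circumference". The synopsis (Section 1.1) lists it in the same way.

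Section 8.1 also uses it as one component of metabolic syndrome, with the criterion "Abdominal circumference: Men of European descent > 94 cm; Women of European descent > 80 cm". The diagnosis rule is "Metabolic Syndrome Diagnosis is established if at least three of the following five criteria are present". The diagnosis then enters the liver fat formula in the same section with a coefficient of 1.18. Section 3 ranks metabolic syndrome and the liver scores as tertiary/exploratory.

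For blood pressure, in the same list, the protocol does say how several readings become one: "The mean of the last two measurements will be used for statistical analysis".

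**The concern.** A change endpoint can be interpreted only if the same quantity is measured each time. Here the instruction names the two extremes of a voluntary manoeuvre. It can be read as two recorded values, as their average, or as a single reading in whichever phase the measurer prefers. None of these is a resting waist, and each depends on how hard the participant breathes in or out.

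Three things follow. Random variation in effort widens the spread of the change score. Physicians and nurses at two centres can read the sentence differently, so one participant could be measured in different phases at different visits. And participants know their arm (Sections 4.1 and 4.2) and produce the effort themselves, so effort could differ between arms at 6 and 18 months. A comparison with a single cut-off also needs a single value, and the protocol does not name one.

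**Working it through.** The protocol gives no waist SD, no expected waist effect and no gap between breathing phases, so there is no stated figure to reproduce. The firm part of the point comes from setting the passages side by side. The arithmetic only illustrates size and rests on assumptions.

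**Text check**

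- Site: fixed in Section 8.1.
- Breathing phase: two opposite phases named, both maximal.
- Number of readings and reduction to one value: not stated for waist; stated for blood pressure in the same list.
- Uses that need one value: the change endpoint (Section 3) and the 94/80 cm criterion (Section 8.1).

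**Noise in the change score**

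Assume effort adds an independent error with SD 2 cm to each reading. A change score uses two readings, so the added component is √2 × 2 = 2.8 cm, with variance 8 cm². It combines in quadrature with the change SD s that would otherwise apply: new SD = √(s² + 8).

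| Assumed s (cm) | New SD (cm) | Rise (cm) |
|---|---|---|
| 4 | √24 = 4.9 | 0.9 |
| 5 | √33 = 5.7 | 0.7 |
| 6 | √44 = 6.6 | 0.6 |
| 8 | √72 = 8.5 | 0.5 |

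The 2.8 cm is therefore a component; the SD itself rises by about 0.5 to 0.9 cm.

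**A shift in one arm only**

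Section 9.2 plans 60 per arm with 15% loss: 60 × 0.85 = 51. Suppose there is no true effect but phase or effort shifts one arm by b cm. With SE = s√(2/51), the chance of p < 0.05 is Φ(b/SE − 1.96) + Φ(−b/SE − 1.96). For s = 5 and b = 1, SE = 0.99 and the chance is about 17%.

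| b (cm) | s = 4 | s = 5 | s = 6 | s = 8 |
|---|---|---|---|---|
| 1 | 24% | 17% | 13% | 10% |
| 2 | 71% | 52% | 39% | 24% |

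These values of b are hypothetical; nothing in the protocol shows that such a shift will occur. A shift that is equal in both arms causes no bias.

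**The cut-off**

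Assume waist is normal with SD 11 cm and the phases differ by g. The share whose waist criterion depends on the phase is the probability of lying within g/2 of the cut-off.

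| Mean above cut-off (cm) | g = 2 cm | g = 5 cm |
|---|---|---|
| 2 | 7% | 18% |
| 10 | 5% | 12% |
| 15 | 3% | 7% |
| 20 | 1% | 4% |

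Fewer diagnoses than waist criteria would change, because waist decides the diagnosis only in someone who meets exactly two of the other four criteria.

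**The case against.** **Blinding.** A reader might infer assessor bias from the open-label design. The documents do not support that as it stands. Section 8.1, after the assessment table, says that evaluators are blinded and come from outside the research team. Section 6.3 plans no blinding of participants or staff, so the two sections are in tension, but the statement cannot be ignored. Nor can allocation influence baseline waist: Section 1.3 places anthropometry at Assessment 1, before randomization. What remains is narrower: participants' own effort at 6 and 18 months, which evaluator blinding does not remove. It is a possibility that the documents do not quantify.

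**Reduction to one value.** How readings are combined is often left to an analysis plan or measurement manual, and Section 10.1.8 provides staff training in data collection. That is fair as far as averaging goes. The protocol itself, however, fixes the maximal manoeuvre, and an averaging rule added later would not remove the dependence on effort. The claim that two separate values are always recorded also goes too far; the firm point is the ambiguity.

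**Metabolic syndrome.** A reader might infer that the diagnosis and the liver fat score are seriously compromised. Entry requires BMI above 27 (Section 5.1), so many waists should lie well above the cut-offs. Any three of five criteria suffice, the other four can be met through treatment, and the endpoint is exploratory. This objection largely stands.

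**Weight of the endpoint.** Waist is not in the list of secondary endpoints in Section 9.4.3. It is still named as one in Sections 1.1 and 3, so it needs a definition.

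**Conclusion.** The point holds as a minor measurement defect. The protocol states a waist method that names two opposite maximal-effort phases and gives no single value for the endpoint or the cut-off. The result is avoidable noise, room for inconsistent phases between staff, sites or visits, and some room for participants who know their arm to vary their effort after randomization.

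Its size cannot be taken from the documents. Under an assumed effort SD of 2 cm per reading, independent between visits, a change SD of 4 to 8 cm becomes about 4.9 to 8.5 cm. A spurious difference between arms would need effort or phase to differ by arm, which is possible but not shown. The effect on metabolic syndrome is probably small. The primary endpoint and the sample size are unaffected.

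**What to change.** In Section 8.1, replace the breathing instruction by one defined value: waist at the site already stated, at the end of a normal, unforced expiration, as the mean of two readings, with the same method in both arms and at T0, 6 and 18 months. State that this value is used for both the endpoint and the metabolic-syndrome criterion.

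For any participant already measured under the present wording, record both phases and use their mean at every visit. Changing such a participant to normal expiration later would mix methods within one change score and create the inconsistency that the fix is meant to remove.

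The cost is one sentence in the protocol and in the measurement instructions. If measurement has begun, the small downside is two methods across participants. Each participant keeps one method throughout, and randomization should balance the two methods between arms.

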- **NAFLD Fibrosis Score:** The identification and quantification of fibrosis are clinically relevant since fibrosis is associated with an unfavorable clinical prognosis. An NFS > 0.676 indicates the presence of advanced fibrosis (*Angulo et al., 2007; Kotronen et al., 2009*). The calculation is determined using the following formula:

$$-1.675 + 0.037 \times \text{Age (years)} + 0.094 \times \text{BMI (kg/m}^2\text{)} + 1.13 \times \text{IFG/diabetes (Yes = 1 / No = 0)} + 0.99 \times \text{AST/ALT ratio} - 0.013 \times \text{Platelets (\times 10}^9\text{/L)} - 0.66 \times \text{Albumin (g/dL)}$$

c) Healthy lifestyle habits

- **Physical activity:** Physical activity will be assessed using the International Physical Activity Questionnaire (IPAQ). It consists of seven questions regarding the frequency, duration, and intensity of physical activity (moderate and vigorous) performed during the previous seven days, as well as walking and sitting time on a typical workday. The questionnaire may be administered through face-to-face interview, telephone interview, or self-administered survey (*Mantilla Toloza & Gómez-Conesa, 2007*).
- **Nutritional and energy composition:** The *24-hour dietary recall questionnaire* will be administered at each biweekly visit. This questionnaire is a reference tool in most

nutritional studies (*Block, 1982; Fanelli & Stevenhagen, 1986; Gersovitz et al., 1978; Madden et al., 1976*), and will be used to determine the daily intake of each type of food (*Freedman et al., 2017*).

- **Smoking habits:** Using a study-specific questionnaire, participants will be directly asked: *Do you smoke?* (Yes/No). If the response is affirmative, participants will be asked: *How many cigarettes do you smoke per day?*
- **Alcohol consumption:** Alcohol intake will be quantified using a questionnaire combined with a standardized alcohol unit conversion calculator. Participants will be asked about their consumption of different alcoholic beverages during the previous seven days. Using the conversion calculator, the total alcohol content (in ml of pure alcohol) will be estimated to obtain the average daily alcohol intake (*Cálculo: Cuantificación Del Consumo de Alcohol - Fisterra, n.d.; Valencia-Martín et al., 2014*).
- **Circadian habits:** Using a study-specific questionnaire, participants will be directly asked: *What time did you go to bed yesterday?* and *How many hours did you sleep today?*

d) Quality of life

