Potential participants will receive an invitation to take part in the study during their last medical consultation (in person or by telephone) by their physician, nurse, or the principal investigator. They will then be scheduled for a screening visit with a member of the research team, following completion of the screening blood test. Patients will be informed of the necessary requirements for the laboratory tests (fasting status and first morning urine sample) as well as the location where they will be carried out (extraction and laboratory areas of each primary care center).

Screening and Study Inclusion Visit

During this visit, eligibility criteria will be assessed to determine whether patients meet the study selection requirements. Participants who fulfill the criteria will receive a detailed explanation of the study objectives and the implications of participation. They will be provided with the study information sheet and, if they agree to participate, will sign an informed consent form for data collection throughout the study. If consent is obtained, a physical examination (anthropometric measurements) will be performed, sociodemographic variables will be recorded, and participants will complete the questionnaires assessing quality of life, physical activity, nutritional status, and lifestyle habits (including substance use). Additionally, appointments will be scheduled for all participants to undergo the imaging test (Carotid ultrasonography).

Laboratory Tests

Blood and urine analyses will be performed at three different time points during the study: at baseline, at the end of the intervention, and 12 months after completion of the intervention. These analyses do not involve any additional procedures, as they are part of the routine clinical practice for monitoring and follow-up of all patients with type 2 diabetes mellitus (T2DM) in primary care. No requests, extractions, or analyses will be conducted outside of standard clinical care. The laboratory tests will include: Complete blood count, HbA1c, Creatinine, Glomerular filtration rate, GOT (AST), GPT (ALT), GGT, Ionogram, Lipid profile (Total cholesterol, HDL, LDL,

Triglycerides, Apo B100), Fasting insulin, Anti-GAD antibodies (only at baseline), Urine: sediment and albumin/creatinine ratio.

Imaging Diagnosis: Carotid ultrasonography

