As part of the cardiovascular risk factor assessment, three ultrasound examinations of the carotides will be performed during the study: at baseline, at the end of the intervention, and 12 months after the completion of the intervention.

	1st Examination and Sample Collection T0 (Baseline / Start of Intervention)	Follow-up Visits	2nd Examination and Sample Collection T-6 months (End of Intervention)	3rd Examination and Sample Collection T-18 months (12 months after End of Intervention)
Questionnaires and Assessment Scales				
24-Hour Recall	X	X	X	X
SF36	X		X	X
IPAQ	X		X	X
Tobacco consumption	X	X	X	X
Alcohol consumption	X	X	X	X
Circadian cycle	X	X	X	X
Physical Examination (Anthropometric Measurements)				
Weight	X	X	X	X
Height	X			
Abdominal circumference	X	X	X	X
Blood Analysis				
Complete blood count ^a (CBC ^a)	X		X	X
C-Reactive protein ^a (CRP ^a)	X		X	X
HbA1c	X		X	X
Creatinine ^a	X		X	X
Glomerular filtration rate ^a (GFR ^a)	X		X	X
Aspartate Aminotransferase (AST)	X		X	X

Alanine Aminotransferase (ALT)	X		X	X
Gamma-Glutamyl Transferase (GGT)	X		X	X
Alkaline Phosphatase ^a (ALP ^a)	X		X	X
Amylase ^a	X		X	X
Total Blood Protein ^a	X		X	X
Electrolyte Panel ^a	X		X	X
Calcium ^a	X		X	X
Phosphate ^a	X		X	X
Lipid Profile (Total Cholesterol, HDL, LDL, Triglycerides, Apo B100)	X		X	X
Basal C-Peptide ^a	X		X	X
Anti-GAD Antibodies (GAD Ab)	X			
TSH ^a	X		X	X
Free T4 ^a (Free Thyroxine ^a)	X		X	X
CA 19.9. ^a	X		X	X
Urine Analysis				
Urine Sediment ^a	X		X	X
Albumin/Creatinine Ratio ^a	X		X	X
Imaging Test (Ultrasound)				
Carotid ultrasonography	X		X	X
Type 2 Diabetes Management and Monitoring				
Hypoglycemia episode(s)		X	x	
Hyperglycemia episode(s)		X	x	

^a Parameters to assess the participant's general health status. These parameters are included in the routine monitoring of a person with type 2 diabetes (T2DM).

^b Only in cases of a discordant relationship between HbA1c values and plasma glucose.

Examinations, laboratory tests, imaging studies, and questionnaires will be conducted at the patient's primary care center (CAP Barceloneta or CAP Larrard) by healthcare personnel (physician/nurse according to the test and training) during regular working hours. Blinding will be implemented for the evaluators, as all tests and questionnaires will be carried out by personnel not

involved in the research team and not responsible for delivering the intervention, with no knowledge of the participant's assignment to group A or B in the study.

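### The NAFLD Fibrosis Score needs serum albumin, which no laboratory list names, and the Liver Fat Score bands need reconciling with the fibrosis cut-off; only exploratory liver endpoints are affected

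*Protocol*

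**What the plan says.** Section 3 (Tertiary/Exploratory) lists change at 6 and 18 months in metabolic syndrome, "NAFLD Fatty Liver Index, and NAFLD Fibrosis Score". Section 8.1 describes both liver scores among the secondary outcome variables and commits to recording those at baseline, end of intervention and 12 months later.

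- **Liver Fat Score (8.1).** The formula uses metabolic syndrome, T2DM (coded 2 or 0), fasting insulin, AST and AST/ALT. It is read as "< -1.455 low risk, -1.455 to 0.675 intermediate risk, > 0.675 high risk".
- **Fibrosis Score (8.1).** The formula uses age, BMI, impaired fasting glucose or diabetes, AST/ALT, platelets and albumin in g/dL. Its cut-off is "An NFS > 0.676 indicates the presence of advanced fibrosis".
- **Laboratory Tests text (8.1).** The list closes with "Fasting insulin, Anti-GAD antibodies (only at baseline), Urine: sediment and albumin/creatinine ratio". The same paragraph states: "No requests, extractions, or analyses will be conducted outside of standard clinical care".
- **Assessment table (8.1).** The nearest blood item is "Total Blood Protein". The only row naming albumin is the urine ratio.
- **Schedule of Activities (1.3).** The laboratory row gives HbA1c, glucose, insulin and lipids as examples and leaves the list open.

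**The concern.** A score cannot be calculated when one of its inputs is not collected. Serum albumin enters the Fibrosis Score with a sizeable coefficient, yet no list tells the sites to request it. If sites follow the lists, the gap may be noticed only at analysis.

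The second issue is interpretation. Two formulas with different intercepts and largely different inputs carry almost the same upper cut-off, 0.675 and 0.676, one for high risk on a liver-fat score and the other for advanced fibrosis. If the Liver Fat Score were reported by band, the bands should at least separate the people in this trial.

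The third is clerical. Section 3 and Section 8.1 name the liver-fat endpoint differently, so a reader cannot be sure that they mean the same measure.

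**Working it through.** The protocol states no figure to reproduce here. The check has three steps.

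**1. Fibrosis Score inputs against the laboratory lists**

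| Input | Source in 8.1 |
|---|---|
| Age, BMI | recorded at baseline; weight repeated |
| Diabetes status | available |
| AST, ALT | text and table |
| Platelets | if reported with the complete blood count |
| Serum albumin (g/dL) | not in the text, not in the visible table |

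Total protein is a different quantity, and the urine ratio measures excretion. Neither gives albumin in g/dL.

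**2. How much the albumin term matters**

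Assumed example: age 60, BMI 32, diabetes = 1, AST/ALT 0.9, platelets 240.

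Without albumin: -1.675 + 0.037×60 + 0.094×32 + 1.13 + 0.99×0.9 - 0.013×240 = -1.675 + 2.220 + 3.008 + 1.130 + 0.891 - 3.120 = 2.454.

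| Albumin (g/dL) | Score = 2.454 - 0.66×albumin |
|---|---|
| 3.5 | 0.144 |
| 4.0 | -0.186 |
| 4.5 | -0.516 |
| 5.0 | -0.846 |

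The shift from 3.5 to 5.0 is 0.66×1.5 = 0.99. The term cannot be left out or replaced by a constant without changing the score materially.

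**3. Whether the Liver Fat Score bands separate this population**

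With T2DM coded 2 and metabolic syndrome present, the fixed part is -2.89 + 1.18 + 0.45×2 = -0.81, so

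score = -0.81 + 0.15×insulin + 0.04×AST - 0.94×(AST/ALT).

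Insulin values are 5, 10, 15 and 25, within the protocol's normal range of 5 to 25, taken here as mU/L. AST (15, 25, 40 U/L) and AST/ALT (0.7, 1.0, 1.3) are assumptions. This gives 4×3×3 = 36 combinations.

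- Lowest value (insulin 5, AST 15, ratio 1.3): -0.81 + 0.75 + 0.60 - 1.222 = -0.68.
- Highest value (insulin 25, AST 40, ratio 0.7): -0.81 + 3.75 + 1.60 - 0.658 = 3.88.
- Low risk: 0 of 36. High risk: 24 of 36. Intermediate: 12 of 36.

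With AST 25 and ratio 1.0 the score is -0.75 + 0.15×insulin. Low risk then needs insulin below (-1.455 + 0.75)/0.15 = -4.7, which is impossible, and high risk starts above (0.675 + 0.75)/0.15 = 9.5 mU/L. Even at the most favourable corner, AST 15 with ratio 1.3, the score is -1.432 + 0.15×insulin, and low risk needs insulin below (-1.455 + 1.432)/0.15 = -0.15.

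The band is not mathematically closed. With AST 15 and a ratio of 2.0, outside the assumed range, the score is -2.09 + 0.15×insulin, and insulin below (-1.455 + 2.09)/0.15 = 4.2 would qualify.

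Without metabolic syndrome, still coded T2DM = 2, 3 of 36 values are low risk, all at insulin 5.

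**The case against.** **The lists are not exhaustive.** Fasting plasma glucose, a primary-endpoint variable, is missing from both the laboratory text and the visible table, and fasting insulin is missing from the visible table. Several analytes in the table are missing from the text, and the schedule leaves its list open. In the text copy reviewed, table footnote b has no marked row, so a row may have been lost. This stands as a limit. It supports saying that albumin is not listed, not that it will never be measured. It does not remove the gap, because the text omits albumin independently of the table and an open list gives sites no instruction.

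**The standard-care sentence does not exclude albumin.** This also stands. Nothing in the protocol says whether serum albumin is routine at these centres.

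**Later recovery.** A reader might infer that an omission could never be repaired because samples are destroyed. Section 10.1.4 places destruction after the project analyses are complete, so the protocol does not settle this.

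**Misclassification.** A reader might infer that the Liver Fat Score bands belong to the Fibrosis Score and that participants would be misclassified. The protocol does not show this. It never attaches -1.455 to the Fibrosis Score, gives no other cut-off for the Liver Fat Score, and two scales can share a number. That one source cited for the bands is titled as a fibrosis-score paper is a reason to check, not proof.

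**The floor is specific to a subgroup.** If a participant in remission without metabolic syndrome were coded T2DM = 0, which the protocol does not state, insulin 5 with AST and ALT of 20 gives -2.89 + 0.75 + 0.80 - 0.94 = -2.28, which is low risk. So the bands are not empty for everyone. Participants must, however, have T2DM and a BMI above 27, so metabolic syndrome by the printed three-of-five rule should be common at baseline.

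**No planned analysis uses the bands.** Section 3 asks for change in the indicators, and Section 9 names no analysis of liver-risk categories. This stands and limits the harm to reporting by category.

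**Conclusion.** The point holds in a limited form. As listed, the laboratory tests do not supply serum albumin, so the Fibrosis Score cannot be derived from them, and the missing term is worth about one point across albumin 3.5 to 5.0 g/dL in the example.

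The Liver Fat Score bands need reconciling with the fibrosis cut-off. Their low band is practically unreachable for participants with T2DM and metabolic syndrome, given insulin of 5 to 25 mU/L and the assumed AST and AST/ALT ranges. Continuous change in that score does not depend on the bands. The difference in endpoint name is clerical.

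The documents do not support saying that the Fibrosis Score can never be computed, or that the Liver Fat Score is misclassified. Both measures are exploratory in Section 3. The primary endpoint, the sample size and the main conclusion are untouched.

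**What to change.** 1. Add serum albumin at baseline, 6 and 18 months to the Laboratory Tests text and the assessment table in 8.1, after confirming that it is compatible with the standard-care sentence there. Otherwise drop the Fibrosis Score as an endpoint.
2. Reconcile the Liver Fat Score bands with the Fibrosis Score cut-off and their sources, or remove them. State that the Liver Fat Score is analysed as continuous change, which is how Section 3 already reads.
3. Use one name for the liver-fat endpoint in Sections 3 and 8.1.

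The cost is one analyte on blood already drawn at three scheduled time points, plus wording. No visit or procedure is added. It is best done before baseline samples are taken.
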